11.8. Copanlisib adverse events of special interest

Non-Infectious Pneumonitis

Non-infectious pneumonitis is an adverse event of special interest. In general, non-infectious pneumonitis was symptomatic, with fever, cough, and dyspnea but asymptomatic in some patients. Therefore CT scans may be used to assess for radiographic indications of non-infectious pneumonitis. The CT findings in case of non-infectious pneumonitis were diffuse ground-glass opacities. A bronchoscopy may not show any findings. Non-infectious pneumonitis resolved in all 9 patients, usually within 2 to 4 weeks. No patient died due to non-infectious pneumonitis. In all 9 patients, study drug was interrupted and in 3 patients permanently discontinued due to non-infectious pneumonitis. Interruption of study drug alone improved non-infectious pneumonitis in 1 patient, 1 patient received steroids only, 2 patients received antibiotics only, and 6 patients received antibiotics and steroids. Re-treatment with study drugs was performed in 2 patients, resulting in re-occurrence of non-infectious pneumonitis in 1 of them.

Hyperglycemia

The PI3K/AKT pathway plays a significant role in regulating glucose metabolism. Hyperglycemia is considered as an “on target” effect of copanlisib, and has been commonly observed in patients treated with copanlisib with an incidence approximately 50-70%.

Hypertension

Approximately 42% of patients have post infusion drug related Grade 3 hypertension. There were no cases of Grade 4 hypertension. There was a CTC Grade 3 SAE hypertension. Hypertension was reported in the medical history of 22 out of 76 patients; 16 of them were already receiving antihypertensive treatment at study start. Antihypertensive treatment was administered in 8 treatment naive patients as a consequence of post infusion hypertension, and in 7 patients due to a worsening of already therapy controlled baseline hypertension. Six of the eight naive patients received treatment only on the day of infusion, and 2 naive patients started chronic antihypertensive treatment.

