14.0 BIOSTATISTICS

14.1. Phase I

In the Phase I part the standard 3+3 dose escalation scheme will be used. If none of the initial cohort of 3 has a DLT (defined in Section 9.2) the dose level will be escalated. If one has a DLT that dose level will be expanded with 3 more patients. Dose escalation will stop if 2 or more DLTs are seen at a dose level within the treatment and observation periods as described in Section 9.2. The MTD is defined as the highest dose level at which at most 1 of the 6 patients treated at that level has a DLT. Two dose levels plus a "-1" dose level are planned for this study. The maximum sample size is 18 patients. Toxicity seen after 4 weeks that are likely or definitely related to treatment with study drugs will be collected and evaluated by the investigators.

All patients that stop protocol therapy or have dose reductions due to a DLT will be included in the DLT analysis. If a patient stopped therapy for other reasons and has taken $\leq 75\%$ of planned doses (2 of 3 copanlisib doses and 21 of 28 doses of ibrutinib) in the first cycle then they will be excluded from DLT analysis. In the event that a patient withdraws from the trial due to a reason unrelated to a DLT before completing cycle one, they will be replaced. We expect that less than 10% of patients will be replaced due to insufficient time of treatment. The probability of dose escalation based on various underlying DLT rates (Table 2).

Table 14-1. DLT probability table								
True DLT rate	5%	10%	15%	20%	25%	30%	40%	50%
Probability of escalation	0.97	0.91	0.81	0.71	0.60	0.49	0.31	0.17

It is expected that 2-3 patients will be enrolled per month and so the phase I portion of the trial will be completed in approximately 6 months.

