14.2. Phase II

The primary objective for this phase II cohort is to assess the complete response rate based on best response by 6 months of ibrutinib and copanlisib and the secondary objective is to measure the disease control rate (stable disease, partial response, and complete response), overall response rate (partial and complete response), duration of response, progression and event free survival. A Simon mini-max two stage design will be used with the goal to increase by complete response rate based on best response by 6 months from 20% to 40%. In first stage, if 5 or more of 18 patients have responses, then the trial will proceed to stage 2. In stage 2, additional patients are enrolled to make the total sample size 33. If 11 or more responses are observed, then the combination is deemed promising. Accrual will not be held while the initial 18 patients in the first stage are evaluated for the 6-month response endpoint. The one sided type I error rate is 0.05 and the power is 0.80. A total of 33 patients will be enrolled, though patients treated at MTD/RP2D from phase I portion of the study will be included in the phase II analysis. Expected accrual is 2-3 patients per month and so the phase II portion will be completed within a year.

For other secondary objectives, the event free survival and progression free survival rates will be assessed by the Kaplan-Meier estimation. Event free survival is defined from the date of first dose to progression, or death, and any events including treatment discontinuation for adverse events or severe adverse events whichever came first. Progression free survival is defined from the date of first dose to progression or death, whichever came first. The duration of response will also be assessed by Kaplan-Meier method but on a sub-cohort of patients who showed any response.

To protect patients from excessive toxicity of the treatment during the entire treatment period, several stopping rules are implemented during the study based on the maximum total number of treated patients in both phase I and II (45). **Treatment related Grade ≥ 3 Pneumonitis or Colitis:** 10% unacceptable rate, 2.5% acceptable rate. Trial to hold enrollment if ≥ 4 deaths related to treatment at any point during the study. Otherwise, hold enrollment based on number of treated patients.

Number of treated patients	1	14	33	45
Number of Gr ≥ 3 Pneumonitis/Colitis to stop the trial	1	2	3	4

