Operating characteristics of the early stopping rule for grade ≥ 3 treatment related pneumonitis/colitis:

True tox rate	0.025	0.04	0.055	0.07	0.085	0.1
Probability of claiming treatment too toxic	0.092	0.224	0.377	0.528	0.661	0.767

Treatment related death: 10% unacceptable rate, 2.5% acceptable rate. Trial to hold enrollment if ≥ 4 deaths related to treatment at any point during the study. Otherwise, hold enrollment based on number of treated patients.

Number of treated patients	1	14	33	45
Number of death to stop the trial	1	2	3	4

Operating characteristics of the early stopping rule for treatment related death:

True tox rate	0.025	0.04	0.055	0.07	0.085	0.1
Probability of claiming treatment too toxic	0.092	0.201	0.323	0.444	0.555	0.652

Any one Grade ≥ 3 Treatment non-hematologic Related Toxicity: 60% unacceptable rate, 40% acceptable rate. Trial to hold enrollment if ≥ 25 single toxicity event related to treatment at any point during the study. Otherwise, hold enrollment based on number of treated patients.

Number of treated patients	Number of Gr ≥ 3 non-hematologic toxicity events to stop the trial
1	1
2	2
4	4
5	5
7	6
9	7
10	8
12	9
14	10
16	11
18	12
20	13
22	14
24	15
26	16
28	17
30	18
32	19
34	20
36	21
39	22
41	23
43	24
45	25

Operating characteristics of the early stopping rule for grade ≥ 3 treatment non-hematologic related toxicity:

True tox rate	0.40	0.44	0.48	0.52	0.56	0.60
Probability of claiming treatment too toxic	0.099	0.194	0.339	0.522	0.707	0.854

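### Section 14.2: the printed boundaries for non-hematologic toxicity and for treatment-related death do not have the operating characteristics stated for them (0.432 against 0.099; 0.767 against 0.652)

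*Combined protocol and SAP*

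**What the plan says.** Section 14.2 (Phase II) gives three early stopping rules, "based on the maximum total number of treated patients in both phase I and II (45" patients). Each has an acceptable and an unacceptable rate, a boundary of event counts by number of treated patients, and a six-cell row of probabilities of declaring the treatment too toxic.

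- **Non-hematologic toxicity:** "Any one Grade ≥ 3 Treatment non-hematologic Related Toxicity: 60% unacceptable rate, 40% acceptable rate". The cap is "Trial to hold enrollment if ≥ 25 single toxicity event related to treatment at any point during the study". The boundary column, headed "Number of Gr ≥ 3 non-hematologic toxicity events to stop the trial", starts 1 event at 1 patient, 2 at 2, 4 at 4, 5 at 5, and ends 25 at 45. The stated row runs from 0.099 at a 40% rate to 0.854 at 60%.
- **Treatment-related death:** acceptable 2.5%, unacceptable 10%. The boundary is 1 at 1, 2 at 14, 3 at 33 and 4 at 45 patients. The row under "Operating characteristics of the early stopping rule for treatment related death" runs from 0.092 to 0.652.
- **Grade ≥3 pneumonitis or colitis:** the same target rates and the same boundary as the death rule, but a row from 0.092 to 0.767. The cap in this paragraph reads "Trial to hold enrollment if ≥ 4 deaths related to treatment at any point during the study".

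Section 14.1 describes the 3+3 scheme for the same early patients: "If one has a DLT that dose level will be expanded with 3 more patients".

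**The concern.** Two inconsistencies can be seen without software. First, a table that stops at 1 event in 1 patient stops with probability at least equal to the event rate, so at 40% it cannot have a stopping probability of 0.099. Second, two rules with the same boundary, target rates and maximum of 45 patients must have the same row, yet the death and pneumonitis/colitis rows differ in five of six cells.

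These rules decide whether enrollment is held, and the stated error rates are the grounds on which the rules are accepted. For non-hematologic toxicity, the table that would be applied and the probabilities offered in its support belong to two different rules. Because phase I patients are counted, the first patient on the study could trigger a hold with a single related Grade ≥3 event, while Section 14.1 responds to one DLT by expanding the cohort. Such an early event is not remote: the rule itself treats a 40% rate as acceptable, and Section 11.8 says "Approximately 42% of patients have post infusion drug related Grade 3 hypertension". For deaths, the stated chance of stopping is too low for the boundary shown.

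**Working it through.** **Inputs (all Section 14.2).** Maximum 45 patients.

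- Non-hematologic boundary (patients/events): 1/1, 2/2, 4/4, 5/5, 7/6, 9/7, 10/8, 12/9, 14/10, 16/11, 18/12, 20/13, 22/14, 24/15, 26/16, 28/17, 30/18, 32/19, 34/20, 36/21, 39/22, 41/23, 43/24, 45/25.
- Death and pneumonitis/colitis boundary: 1/1, 14/2, 33/3, 45/4.

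The caps of 25 and 4 equal the last rows and add nothing.

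**Method.** Exact binomial recursion, one independent yes/no event per patient with probability p. Let f(n,k) be the probability of reaching patient n with k events and no stop:

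f(n,k) = (1−p)·f(n−1,k) + p·f(n−1,k−1) for k below the boundary.

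Probability at or above the boundary is added to the stopping probability. Each row applies up to and including its patient count; looking only at the listed counts gives the same results.

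**Step 1: check the convention on the pneumonitis/colitis rule.**

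| True rate | 0.025 | 0.04 | 0.055 | 0.07 | 0.085 | 0.10 |
|---|---|---|---|---|---|---|
| Stated | 0.092 | 0.224 | 0.377 | 0.528 | 0.661 | 0.767 |
| Computed | 0.097 | 0.224 | 0.377 | 0.528 | 0.661 | 0.767 |

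Five of six cells match. Without the 1/1 row the last cell would be 0.759, so the plan's own calculation treats a 1-of-1 row as active.

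**Step 2: non-hematologic rule.** At p = 0.40 the 1/1 row stops with probability 0.40. The later rows add 0.032, giving 0.432. (While 1/1 operates, 2/2 has no effect: a trial that passes patient 1 has at most one event after two patients.)

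| True rate | 0.40 | 0.44 | 0.48 | 0.52 | 0.56 | 0.60 |
|---|---|---|---|---|---|---|
| Stated | 0.099 | 0.194 | 0.339 | 0.522 | 0.707 | 0.854 |
| Table as printed | 0.432 | 0.509 | 0.609 | 0.724 | 0.833 | 0.918 |
| Without 1/1 only | 0.212 | 0.306 | 0.439 | 0.599 | 0.756 | 0.879 |
| Without 1/1 and 2/2 | 0.099 | 0.194 | 0.339 | 0.522 | 0.707 | 0.854 |

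The stated row is that of a table starting at 4/4.

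**Step 3: death rule.**

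| True rate | 0.025 | 0.04 | 0.055 | 0.07 | 0.085 | 0.10 |
|---|---|---|---|---|---|---|
| Stated | 0.092 | 0.201 | 0.323 | 0.444 | 0.555 | 0.652 |
| Boundary as printed | 0.097 | 0.224 | 0.377 | 0.528 | 0.661 | 0.767 |

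At 10% the gap is 0.767 − 0.652 = 0.115. Dropping the 1/1 row (0.759 at 10%) or ending at 33 patients (0.700) does not give the stated row. A boundary of 2 by 20 and 3 by 27 patients, ending at 27, reproduces all six cells, but no such boundary appears in the plan, so that origin is only inference.

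**Step 4: other readings.** Carrying each row forward until the next gives 0.526 (non-hematologic, 40%) and 0.922 (death, 10%), further from the stated figures. Applying each row only below its own count, so that 1/1 never acts, gives 0.056 and 0.751, which also miss.

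**Step 5: size of the effect.** If a hold is permanent, the expected number treated at a 40% rate is 26.7 with the printed table and 42.2 without the first two rows. At 42%, the hypertension figure in Section 11.8, the stopping probabilities are 0.468 and 0.140.

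**The case against.** The best counter-argument is that the non-hematologic design is sound and the table merely carries two stray rows, since all six cells match once they go. That is the likely cause, but nothing in the plan suspends those rows, and the instruction is to hold according to the number of treated patients. The table as printed is what a study team would apply.

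For deaths, it can be said that the row is only descriptive, that it is off by 0.005 at the acceptable rate, and that the printed boundary stops more often overall than stated. That stands and makes this part less serious, but whether protection is affected depends on which boundary was intended, which the plan does not settle.

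Other points that stand in part:

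- The 42% figure is a single toxicity from earlier copanlisib experience, and Section 3.0 gives 29% for hypertension. It is an illustration only; the rule's own 40% rate carries the argument.
- The overlap with 3+3 at a 1-of-1 row concerns only the first patient, and the other two rules share it.
- The rule's wording (any one, single toxicity event) could mean each toxicity type is tracked separately. Then 0.432 is a per-type figure, and the mismatch with 0.099 remains.
- The text says hold enrollment while the table headings say stop the trial, so the expected sample sizes depend on what a hold means.

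**Conclusion.** The concern holds. The printed non-hematologic boundary has a false-stop probability of 0.432 at the acceptable rate, more than four times the stated 0.099, and it exceeds the stated figure at every tabulated rate. The death row does not belong to its printed boundary; the gap is 0.005 at 2.5% and 0.115 at 10%. Both rules stop more often than the plan states.

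The figures rest on one independent yes/no event per patient, in order of treatment, up to 45 patients, with each row applied at or up to its listed count. The plan's pneumonitis/colitis row supports that convention. The non-hematologic finding needs less: any reading that applies the 1-of-1 row stops with probability at least 0.40 at a 40% rate. The non-hematologic mismatch is the main reason this must be fixed; the death row is second.

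Two minor slips sit alongside: the 2.5% cell of the pneumonitis/colitis row should read 0.097 rather than 0.092, and that paragraph's cap is expressed in deaths although the rule monitors pneumonitis and colitis.

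**What to change.** The sponsor should confirm the intended boundary for each rule and make boundary and row agree in Section 14.2.

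- **Non-hematologic:** either remove the rows for 1 and 2 patients, so that the stated row stands, or keep them and restate the row as 0.432, 0.509, 0.609, 0.724, 0.833, 0.918. If they are kept, reconcile the 1-of-1 row with the 3+3 scheme in Section 14.1.
- **Death:** if the printed boundary is intended, restate the row as 0.097, 0.224, 0.377, 0.528, 0.661, 0.767. If not, correct the boundary and recompute the row.
- **Minor:** change 0.092 to 0.097 in the pneumonitis/colitis row, and reconcile the event named in that paragraph's cap with the event the rule monitors.

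It would help to state in the same edit that each patient counts once and whether reaching a boundary means a hold or a stop. The cost is protocol wording only: no added patients, visits or data, though some stated figures change or a boundary is corrected.

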11.6. Ibrutinib adverse events of special interest

Hemorrhagic Adverse Events

Fatal bleeding events have occurred in patients treated with ibrutinib. Grade 3 or higher bleeding events (subdural hematoma, gastrointestinal bleeding, hematuria and post procedural hemorrhage) have occurred in up to 6% of patients. Bleeding events of any grade, including bruising and petechiae, occurred in approximately half of patients treated with ibrutinib. The mechanism for the bleeding events is not well understood. Ibrutinib may increase the risk of hemorrhage in patients receiving antiplatelet or anticoagulant therapies.

Subjects in the current study will be monitored closely for hemorrhagic adverse events. Ibrutinib should be held at least 3 to 7 days pre and post-surgery depending upon the type of surgery and the risk of bleeding (please refer to Section 9.7 for further details).

Infection

Fatal and non-fatal infections have occurred with ibrutinib therapy. Grade 3 or greater infections occurred in 14% to 29% of patients. Cases of progressive multifocal leukoencephalopathy (PML) have occurred in patients treated with ibrutinib. Monitor patients for fever and infections and evaluate promptly.

Cytopenias

Treatment-emergent Grade 3 or 4 cytopenias including neutropenia (range, 19 to 29%), thrombocytopenia (range, 5 to 17%), and anemia (range, 0 to 9%) occurred in patients treated with ibrutinib. Monitor complete blood counts monthly.

Atrial Fibrillation

Atrial fibrillation and atrial flutter (range, 6 to 9%) have occurred in patients treated with ibrutinib, particularly in patients with cardiac risk factors, acute infections, and a previous history of atrial fibrillation. Periodically monitor patients clinically for atrial fibrillation. Patients who develop arrhythmic symptoms (e.g., palpitations, lightheadedness) or new onset dyspnea should have an ECG performed. If atrial fibrillation persists, consider the risks and benefits of ibrutinib treatment and dose modification based on recommendations in Section 9.

Hypertension

Hypertension (range, 6 to 17%) has occurred in patients treated with ibrutinib with a median time to onset of 4.6 months (range, 0.03 to 22 months). Monitor patients for new onset hypertension or hypertension that is not adequately controlled after starting ibrutinib. Adjust existing anti-hypertensive medications and/or initiate anti-hypertensive treatment as appropriate.

Secondary Primary Malignancies

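### The Grade ≥3 non-hematologic stopping rule in Section 14.2 is worded in events, but its stated operating characteristics hold only if each patient counts at most once

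*Combined protocol and SAP*

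**What the plan says.** Section 14.2 sets a rule for "Any one Grade ≥ 3 Treatment non-hematologic Related Toxicity", with "60% unacceptable rate, 40% acceptable rate". The rule runs over the 45 patients who may be treated across both phases.

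- The boundary table sets the number of treated patients against a column headed "Number of Gr ≥ 3 non-hematologic toxicity events to stop the trial". Its rows begin 1 in 1, 2 in 2, 4 in 4, 5 in 5, 6 in 7 and 7 in 9, and end at 25 in 45.
- The cap reads "Trial to hold enrollment if ≥ 25 single toxicity event related to treatment at any point during the study".
- The stated probabilities of declaring the treatment too toxic are 0.099, 0.194, 0.339, 0.522, 0.707 and 0.854 at true rates of 0.40, 0.44, 0.48, 0.52, 0.56 and 0.60.

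Nothing in the section says whether a patient counts once or whether repeat events count.

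Section 11.8 states, for copanlisib: "Approximately 42% of patients have post infusion drug related Grade 3 hypertension". The rule names no exception for this event.

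**The concern.** A boundary in events and an operating-characteristic table in rates per patient describe different rules unless no patient can have two events. Here a patient can. Section 4.3 gives copanlisib on three days of each 28-day cycle, and Section 9.1.1 has blood pressure measured before, during and after every infusion. Section 14.2 applies the rules over the whole treatment period. A team that applied the table literally could add repeat Grade 3 events from the same patient and reach a boundary without the patient-level rate being high.

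At stake is the meaning of a hold. The plan accepts about a 10% chance of holding when 40% of patients are affected. If events are counted, that error rate no longer applies, and a hold would not show that more than an acceptable share of patients is affected.

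Two related points concern the same rule. The earliest printed rows do not fit the stated operating characteristics. The protocol's own figure for one drug-related Grade 3 event also lies slightly above the rate that the rule calls acceptable.

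**Working it through.** **Inputs.** From Section 14.2: the boundary b(n), the maximum of 45 patients, the 40% and 60% rates, and the six stated probabilities. From Section 11.8: 42% for hypertension. The repeat fractions in step 3 and the range of other toxicity in step 4 are assumptions, because the documents give no such figures.

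**Method.** Let X be one patient's contribution and S(n) the running total after n patients. The trial holds at the first n with S(n) ≥ b(n). The exact recursion is f_n(s) = Σ_x f_{n−1}(s−x)·P(X=x) for totals below the boundary. The mass reaching b(n) is added to the hold probability and removed.

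**Step 1. Reproduce the plan's figures.** Take X as 0 or 1 with P(X=1) = p, and start the boundary at 4 in 4.

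| True rate p | 0.40 | 0.44 | 0.48 | 0.52 | 0.56 | 0.60 |
|---|---|---|---|---|---|---|
| Stated | 0.099 | 0.194 | 0.339 | 0.522 | 0.707 | 0.854 |
| Recomputed | 0.099 | 0.194 | 0.339 | 0.522 | 0.707 | 0.854 |

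All six agree to three decimals. Of the variants tried, which differed in when the boundary is checked and in how many early rows are dropped, only this version matches all six. The rule was therefore calibrated on one 0/1 outcome per patient.

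**Step 2. Apply the first two rows as printed.** With 1 in 1 in force, the first patient alone triggers a hold with probability p. At p = 0.40 the hold probability is then at least 0.40, so 0.099 is impossible. The full recursion with all rows gives 0.432 at 0.40.

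**Step 3. Count events.** Keep 40% of patients affected, and let a fraction r of those have exactly one further event. Then P(0) = 0.60, P(1) = 0.40(1−r) and P(2) = 0.40r. The expected total at 45 patients is 45 × 0.40 × (1+r) = 18(1+r), against the cap of 25. The boundary starts at 4 in 4. For simplicity, a repeat is booked with the patient's first event.

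| r (assumed) | Expected events at 45 | Hold probability |
|---|---|---|
| 0 | 18.0 | 0.099 |
| 10% | 19.8 | 0.27 |
| 25% | 22.5 | 0.53 |
| 50% | 27.0 | 0.82 |

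The share of patients affected is 40% in every row. Only the counting differs.

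**Step 4. Expected hypertension, on a patient count.** At p = 0.42 the hold probability is 0.140, against 0.099 at 0.40. Suppose other related Grade ≥3 non-hematologic toxicity occurs independently in a fraction q of patients. The affected share is then 1 − 0.58(1−q).

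| q (assumed) | Affected share | Hold probability |
|---|---|---|
| 5% | 0.449 | 0.22 |
| 10% | 0.478 | 0.33 |
| 14% | 0.501 | 0.43 |
| 20% | 0.536 | 0.60 |
| 29% | 0.588 | 0.82 |

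The hold probability reaches 0.50 at an affected share of about 0.515, that is q = 1 − 0.485/0.58, or about 16%.

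**The case against.** **The unit is only loosely worded.** The rule is set by rates, tabulated against treated patients, and headed as any one toxicity. The stated probabilities fit only a patient count. A reader might infer that the rule is known to count repeats, but the documents do not establish that. They leave the unit undefined, with the header and cap saying events and the calibration saying patients. The repeat fractions in step 3 are assumed, and copanlisib is held after a complete response (Section 4.3), which limits exposure for some patients. This softens the charge but does not remove it, because the operative text still differs from the rule that was evaluated.

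**Would the expected toxicity probably halt accrual?** A reader might infer so by adding the ibrutinib figures in Section 11.6 to the 42%: "Grade 3 or greater infections occurred in 14% to 29% of patients", and Grade 3 or higher bleeding in up to 6%. The composite would be 1 − 0.58×0.86×0.94 = 53% to 1 − 0.58×0.71×0.94 = 61%, with hold probabilities of about 0.57 to 0.88. The documents do not support that step. The rule counts treatment-related toxicity, and Section 11.6 gives neither relatedness nor overlap with hypertension. The heading can also be read as one particular toxicity type, in which case nothing is added and the figure stays at 0.14. Section 3.0 also gives hypertension as 29%, without a grade.

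**Should transient hypertension and glucose rises simply be excluded?** That is tempting, since Section 9.2 exempts short-lived post-infusion glucose rises from the DLT definition. It does not exempt Grade 3 hypertension, however. With the boundary unchanged, the remaining infection and bleeding figures give 1 − 0.86×0.94 = 19% to 1 − 0.71×0.94 = 33% and a hold probability of only about 0.002 to 0.03. The rule would then rarely react, so the exclusion cannot be made by wording alone.

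**The consequence is a hold on enrollment,** and Section 9.4 provides for ongoing safety review. That is fair, and it limits the harm of a false trigger.

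**Conclusion.** The point stands in three parts.

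1. **Counting unit: wrong as written.** The wording is in events, and the stated 0.099 to 0.854 apply only to one count per patient. That conclusion rests on an exact reproduction and needs no assumption. Its size does: 0.27, 0.53 or 0.82 instead of 0.10 at the acceptable rate, for assumed second-event fractions of 10%, 25% or 50%.
2. **First two rows: inconsistent with the stated operating characteristics.** Applying them gives 0.43 instead of 0.099 at the 40% rate. This needs no assumption beyond the printed table.
3. **Expected hypertension: a discrepancy to reconcile.** The 42% in Section 11.8 slightly exceeds the 40% acceptable rate, and the rule does not say whether the event counts. On a patient count this alone gives 0.14. Higher values need assumptions about other related toxicity that the documents do not give, so a claim that accrual would probably halt is not supported.

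**What to change.** In Section 14.2:

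- In the boundary table header and in the cap sentence, replace the event wording with *patients with at least one treatment-related Grade ≥3 non-hematologic toxicity, each patient counted once*. This makes the count match the one used for the stated operating characteristics. The cost is that repeat events in one patient no longer move the rule.
- Reconcile the 1 in 1 and 2 in 2 rows with the operating characteristics: either remove them, or keep them and replace the stated probabilities with those that include them. If kept, the hold probability at the acceptable rate is 0.43, and the plan should say that this is intended.
- Reconcile Sections 11.8 and 14.2 by stating whether expected post-infusion Grade 3 hypertension counts. If it does not, reconsider the acceptable and unacceptable rates and the boundary for what remains, and recompute the operating characteristics.

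The first change is wording only. The second needs a short edit or one recalculation. The third needs a decision by the sponsor and, if the event is left out, a new boundary calculation.
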